1	Antifungal Medication ¹	Medical claim with an NDC, HCPCS, generic name or CPT code in the IP, non-IP, or pharmacy setting for antifungal medications (dichotomous)	14 days prior to index date to 1 day prior to index date Index date to the end of follow-up
1	Intravenous immunoglobulin ¹	Medical claim with an NDC, HCPCS, generic name, CPT, or ICD-10 procedure code in the IP, non-IP, or pharmacy setting for intravenous	14 days prior index date to 1 day prior to index date

Objective	Variable	Definition	Assessment Period(s)
		immunoglobulin administration (dichotomous)	Index date to the end of follow-up
1	Other hematological malignancies	Medical claim with an ICD-10 code in the IP or non-IP setting for hematological malignancies other than MM (dichotomous)	MM diagnosis to 1 day prior to index date
1	Any non-hematological malignancy	Medical claim with an ICD-10 code in the IP or non-IP setting for non-hematological malignancies (dichotomous)	MM diagnosis to 1 day prior to index date
1	Plasma cell leukemia	Medical claim with an ICD-10 code in the IP or non-IP setting for plasma cell leukemia (dichotomous)	MM diagnosis to 1 day prior to index date
1	Bone lesions	Medical claim with an ICD-10 code in the IP or non-IP setting for bone lesions (dichotomous)	MM diagnosis to 1 day prior to index date
1	Peripheral neuropathy	Medical claim with an ICD-10 code in the IP or non-IP setting for peripheral neuropathy (dichotomous)	MM diagnosis to 1 day prior to index date
1	Any infection	Medical claim with an ICD-10 code in the IP or non-IP setting for any infection of the following types (dichotomous): COVID-19 Sinusitis Bronchitis Adenoviral pneumonia Cytomegaloviral pneumonitis Other Pneumonia Upper respiratory tract infection	MM diagnosis to 1 day prior to index date

Objective	Variable	Definition	Assessment Period(s)
		
Sepsis
 
Cytomegaloviral infection
 
Pneumocystis jiroveci pneumonia (PJP)
 
Hepatitis C
 
Hepatitis B
 
Other infectious hepatitis
 
Helicobacter pylori
 
Candida esophagitis
 
Urinary tract infection
	
1	Use of intravenous anti-infective	Medical claim with an NDC code generic name, CPT, or HCPCS code in the IP, non-IP, or pharmacy setting for anti-infective where the route of administration is intravenous for an intravenous anti-infective (dichotomous)	MM diagnosis to 1 day prior to index date

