Intravenous immunoglobulin	Baseline characteristic - Treatments, Dexamethasone	Claims data	
HCPCS (Mapped via Athena – OHDSI using brand name): J1556, C9130, J1557, J1559, C9270, Q4097, Q4092, Q4091, Q4088, Q4087, J1572, J1569, J1568, J1562, J1459, J1576, J1555, C9072, J1551, J1554, J1558
 
Brand Name (mapped to NDC codes via First Data Bank): Asceniv, Bivigam, Gammagplex, Privigen, Octagam, Flebogamma/Flebogamma Dif, Panzyga, Gammagard Liquid, Flebogamma, Gamunex, Gammagard N, LAndoglobulin, Polygam S/D, Gammagard S-D, Gammagard S/D, Gammagard,
	
Mayo Clinic (2024) Athena – OHDSI

			Panglobulin, Carimune, Carimune Nf Nanofiltered, Venoglobulin-S, Iveegam En, Flebogamma Dif	
Other hematological malignancies	Baseline characteristic - Clinical	Claims data	ICD-10 Diagnosis: Lymphoma; malignant plasma cell neoplasm; leukemia; other and unspecified malignant neoplasms of lymphoid, hematopoietic, and related tissue; and myelodysplastic syndrome: C81-C96, D46 (Excluding C90.0x)	Maziarz et al. (2024)
Any non-hematological malignancy	Baseline characteristic - Clinical	Claims data	ICD-10 Diagnosis: C0x.x, C1x.x, C2x.x, C30.x, C31.x, C32.x, C33.x, C34.x, C37.x, C38.x, C39.x, C40.x, C41.x, C43.x, C45.x, C46.x, C47.x, C48.x, C49.x, C50, C51-C58.x, C60-63.x, C76.x, C80.1	Glasheen et al. (2019)
Plasma cell leukemia	Baseline characteristic - Clinical	Claims data	ICD-10 Diagnosis: C90.1x	Wu et al. (2017)
Graft vs host disease	Baseline characteristic - Clinical	Claims data	ICD-10 Diagnosis: D89.81x	Huang et al. (2023)
Benign bone lesions	Baseline characteristic - Clinical	Claims data	ICD-10 Diagnosis: D16.0-D16.9, M85.0, M85.4-M85.6, D48.0	Muran et al. (2023)
Peripheral neuropathy	Baseline characteristic - Clinical, AE	Claims data	ICD-10 Diagnosis: G90.50, G90.513, G90.511, G90.512, G90.519, G90.521, G90.529, G90.522, G90.523, G90.59, G54.0, G55, G54.2, G54.4, E08.41, E09.41, E10.41, E11.41, E13.41, G57.70, G57.71, G57.72, G57.73, G59, G57.80, G57.81, G57.82, G57.83, G58.8, G58.9, G64, G61.0, M05.50, M05.511, M05.512, M05.519, M05.521, M05.522, M05.529, M05.531, M05.532, M05.539, M05.541, M05.542, M05.549, M05.551, M05.552, M05.559, M05.561, M05.562, M05.569, M05.571, M05.572, M05.579, M05.59, E08.40, E08.42, E09.40, E09.42, E10.40, E10.42, E11.40, E11.42, E13.40, E13.42, G13.0, G13.1, A36.83, A52.15, G63, M34.83, G62.1, G61.1, G62.0, G62.2, G62.82, G61.81, G62.81, G61.89,	Song et al. (2019)

PFIZER CONFIDENTIAL

Redacted

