			G62.89, G61.9, G62.9, H46.3, M54.10, M54.18, M79.2, R20.0, R20.1, R20.2, R20.3, R20.8, R20.9	
Any infection	Baseline characteristic - Clinical	Claims data	An ICD-10 Diagnosis Code for any of the following types of infections. See the rows below for codes for each infection type. COVID-19, Adenoviral pneumonia, Cytomegaloviral pneumonitis, Other Pneumonia, Upper respiratory tract infection, Sepsis, Cytomegaloviral infection, PJP, Hepatitis C, Hepatitis B, Other infectious hepatitis, Helicobacter pylori, Candida esophagitis, Urinary tract infection	N/A
Use of intravenous anti-infective	Baseline characteristic - Clinical	Claims data	See “Antivirals,” “Antibiotics,” and “Antifungals” and where service category = injection/infusion drugs or where route = injectable or route array has injectable in it OR HCPCS/CPT codes that indicate IV administration of an anti-infective	N/A
Absolute neutrophil count (for Neutropenia)	Baseline characteristic - Clinical, AE	Claims data	White blood cell count x the percentage of neutrophils White blood cell count: Results_value in the lab results table where the result_abbrev is wbc and result_units are thousand per μ L Percent Neutrophil: Results_value in the lab results table where the result_abbrev is neutrophils percent and result_units are percent White blood cell count and percent neutrophil results must occur on the same day	Severe Chronic Neutropenia International Registry
Neutropenia	Baseline characteristic - Clinical, AE	Claims data	ICD-10 Diagnosis: D70.x or Absolute neutrophil count < 1500 cells per μ L	Kim et al. (2022) Lustberg et al. (2012)

PFIZER CONFIDENTIAL

Redacted

Hypercalcemia	Baseline characteristic - Clinical	Claims data	ICD-10 Diagnosis: E83.52 or value in the GDD table where test is hypercalcemia and result_units are mg/dL and result_value is > 11.5	Kumi et al. (2024) CTCAE v6 (2020)
Hepatotoxicity	Baseline characteristic - Clinical, AE	Claims data	ICD-10 Diagnosis: K71.x	Banerjee et al. (2023)
Amyloidosis	Baseline characteristic - Clinical	Claims data	ICD-10 Diagnosis: E85.4x, E85.8x, E85.9x	Quock et al. (2018)
Hypertension	Baseline characteristic - Clinical	Claims data	ICD-10 Diagnosis: I10x-I15x	Angier et al. (2019)
Extramedullary plasmacytoma	Baseline characteristic - Clinical	Claims data	ICD-10 Diagnosis: C90.2x	Ellington et al. (2021)
CCI score	Baseline characteristic - Clinical	Claims data	See components below	Glasheen et al. (2019)

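### The code list for *Other hematological malignancies* removes only C90.0x, so plasmacytoma and plasma cell leukemia codes count as another blood cancer; *Any non-hematological malignancy* separately omits C64-C75

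*Protocol*

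**What the plan says.** Protocol Section 9.3, Table 2, defines *Other hematological malignancies* as "Medical claim with an ICD-10 code in the IP or non-IP setting for hematological malignancies other than MM (dichotomous"). Annex 2 supplies the codes. It names the groups as "Lymphoma; malignant plasma cell neoplasm; leukemia; other and unspecified malignant neoplasms of lymphoid" and so on, and ends with "hematopoietic, and related tissue; and myelodysplastic syndrome: C81-C96, D46 (Excluding C90.0x").

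Two further Annex 2 rows draw on the same block. Plasma cell leukemia is "ICD-10 Diagnosis: C90.1x", reported through its own Table 2 row ("Medical claim with an ICD-10 code in the IP or non-IP setting for plasma cell leukemia (dichotomous")). Extramedullary plasmacytoma is "ICD-10 Diagnosis: C90.2x", the only Annex 2 entry matching the Table 2 row on extramedullary disease.

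For *Any non-hematological malignancy*, the Annex 2 list ends with "C51-C58.x, C60-63.x, C76.x, C80.1".

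Section 9.3 refers the reader to Annex 2 for the full code list, and Section 9.8 says that measures will be coded as described in the protocol and the protocol strictly followed. The lists are therefore what will be run.

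**The concern.** Every patient in the cohort must have myeloma, defined as C90.0x. Within that cohort the protocol reports extramedullary disease as a clinical characteristic. The same claim then also marks the patient as having a blood cancer other than myeloma. A patient with advanced myeloma and no second cancer would appear in the table as having one.

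The solid-tumour row has the opposite fault. Its name and Table 2 definition are unrestricted, but part of the code range is missing.

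Section 9.9 warns that the light eligibility criteria may let in patients with other malignancies. These two Objective 1 rows are where a reader would look to see how often that happened. One is too high and the other too low, so they do not share a direction that a reader could allow for. Both are repeated in the teclistamab cohort.

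**Working it through.** The protocol gives no expected prevalence for either row, so there is no figure to reproduce. The check is of code membership.

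**1. Blood cancer row.** Rule as written: code in C81-C96 or D46, and not C90.0x. Applied to test codes, beside two possible corrections:

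| Code | As written | Also minus C90.1x, C90.2x | Minus all C90.x |
|---|---|---|---|
| C90.00, C90.01 | not counted | not counted | not counted |
| C90.10 | counted | not counted | not counted |
| C90.20 | counted | not counted | not counted |
| C90.30 | counted | counted | not counted |
| C83.3, C92.0, D46.9 | counted | counted | counted |

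**2. Is the overlap certain?** Yes. In Table 2 the rows for other hematological malignancies, plasma cell leukemia and extramedullary disease all use diagnosis codes on inpatient or non-inpatient claims. All three run from the myeloma diagnosis to the day before index. The codes of the last two are subsets of the first, so anyone flagged in them is flagged in the first.

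**3. Size per patient.** One patient who qualifies only through C90.1x or C90.2x adds 100/n percentage points. Section 9.5 cites 56 patients with an elranatamab claim: 100/56 = 1.8 points. The step shrinks as refreshes add patients.

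**4. Illustration only.** Let t be the true share with another blood cancer and o the share of the remaining patients carrying only C90.1x or C90.2x. The reported share is t + (1 - t) × o. Both inputs are assumptions; the range is t = 3-5% and o = 2-20%.

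- t = 3%, o = 2%: 0.03 + 0.97 × 0.02 = 4.9%
- t = 5%, o = 2%: 0.05 + 0.95 × 0.02 = 6.9%
- t = 3%, o = 20%: 0.03 + 0.97 × 0.20 = 22.4%
- t = 5%, o = 20%: 0.05 + 0.95 × 0.20 = 24.0%

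The ratio of reported to true runs from 6.9/5 = 1.4 to 22.4/3 = 7.5 within these assumptions.

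**5. Can a reader undo it from the table?** Not exactly. With A patients in the blood cancer row, P in the plasma cell leukemia row and E in the extramedullary row, the count without C90.1x and C90.2x lies between max(0, A - P - E) and A. Patients may sit in both P and E, or carry a lymphoma or leukemia code as well.

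**6. Solid-tumour row.** The list covers C60-C63 and then C76. C64-C75 lies between two blocks that the row itself treats as non-hematological. No other malignancy row in Annex 2 picks it up: the metastatic row lists C77-C79, C80.0 and C80.2, and the blood cancer row starts at C81. The *Any malignancy* component of the Charlson index has the same jump, but it also contains C9x.x. Any patient with a myeloma code in the 180-day window is therefore already scored there, and the gap has little effect on the index. The stand-alone row has no such cover.

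**The case against.** The strongest reply is that text and codes agree if read literally. The protocol defines myeloma as C90.0x, Table 2 says other than myeloma, and Annex 2 removes exactly C90.0x. The row also names malignant plasma cell neoplasms as an included group, which after that removal can only mean the rest of C90. The wording may come from the cited source. This stands in part. It weakens the plasma cell leukemia half, since leukemia is named in the row too. It is less persuasive for C90.2x, because the protocol presents extramedullary disease as a feature of these myeloma patients, and no text says that the overlap is intended.

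A second reply is that overlapping rows are normal in this protocol: CAR-T products also count as BCMA-directed therapy, and CD38 antibodies also count as monoclonal antibodies. That is true, but in those cases the narrower item belongs to the broader category in meaning as well as in code.

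A third is that the C63-to-C76 jump appears in two lists citing the same source and so looks inherited. That would explain the gap in the index. It does not make a row named for any such malignancy complete.

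A reader might also infer that the blood cancer row will be inflated several-fold. The documents do not support a multiplier, because every prevalence behind one is assumed.

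**Conclusion.** The point holds, and its scope is limited. As coded, *Other hematological malignancies* necessarily includes every patient with C90.1x or C90.2x, so it can only be overstated as a measure of blood cancers other than myeloma. The extramedullary half is the stronger one. *Any non-hematological malignancy* cannot detect C64-C75, so it can only be understated.

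Both directions follow from the protocol's own code lists. The sizes do not: the first is about 1.8 percentage points per affected patient at n = 56, and the second cannot be sized at all.

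A reader might infer that the study's results are compromised. They are not. Neither row enters eligibility, treatment exposure, resource use and cost, adverse events, time to next treatment or survival, and no formal comparison between cohorts is planned. The consequence is two misleading lines in the baseline table, on the question that Section 9.9 raises.

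**What to change.** In Annex 2, extend the exclusion for *Other hematological malignancies* to C90.1x and C90.2x, and keep plasma cell leukemia and extramedullary disease as separate rows. Removing all of C90.x is not a safe shortcut: C90.3x has no row of its own in Table 2 or Annex 2, and those patients would vanish from the table. If it is excluded, add a row for it. If the sponsor does intend to count other plasma cell neoplasms, the minimum is to rename the row and footnote the overlap.

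Add C64-C75 to *Any non-hematological malignancy*. Then either align the Charlson *Any malignancy* list or state that it follows the cited index unchanged.

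The cost is two code-list edits and a rerun of two baseline rows per cohort at the next refresh, plus a rerun of the index if its list is changed. Version 2.0 already edited the Charlson malignancy list to add myeloma codes, so this is a familiar kind of amendment.

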1	Chronic pulmonary disease	Medical claim with an ICD-10 code in the IP or non-IP setting for chronic pulmonary disease (dichotomous)	180 days prior to index date to index date
1	Rheumatic disease	Medical claim with an ICD-10 code in the IP or non-IP setting for rheumatic disease (dichotomous)	180 days prior to index date to index date
1	Peptic ulcer disease	Medical claim with an ICD-10 code in the IP or non-IP setting for peptic ulcer disease (dichotomous)	180 days prior to index date to index date
1	Liver disease	Medical claim with an ICD-10 code in the IP or non-IP setting for liver disease (dichotomous)	180 days prior to index date to index date
1	Diabetes	Medical claim with an ICD-10 code in the IP or non-IP setting for diabetes (dichotomous)	180 days prior to index date to index date
1	Renal disease	Medical claim with an ICD-10 code in the IP or non-IP setting for renal disease (dichotomous)	180 days prior to index date to index date
1	Hemiplegia or paraplegia	Medical claim with an ICD-10 code in the IP or non-IP setting for hemiplegia or paraplegia (dichotomous)	180 days prior to index date to index date
1	Human immunodeficiency virus	Medical claim with an ICD-10 code in the IP or non-IP setting for human immunodeficiency virus (dichotomous)	180 days prior to index date to index date
1	Metastatic solid tumor	Medical claim with an ICD-10 code in the IP or non-IP setting for metastatic solid tumor (dichotomous)	180 days prior to index date to index date

Objective	Variable	Definition	Assessment Period(s)
1	Albumin serum	Lab event with albumin serum as the test name and g/dL as the result units (dichotomous)	180 days prior to index date to index date
		Most recent numeric value to index date of a lab event with albumin serum as the test name and g/dL as the result units (continuous)	
1	Alanine aminotransferase (ALT)	Lab event with ALT as the test name and IU/L as the result units (dichotomous)	180 days prior to index date to index date
		Most recent numeric value to index date of a lab event with ALT as the test name and IU/L as the result units (continuous)	
1	Aspartate aminotransferase (AST)	Lab event with AST as the test name and IU/L as the result units (dichotomous)	180 days prior to index date to index date
		Most recent numeric value to index date of a lab event with AST as the test name and IU/L as the result units (continuous)	

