Diabetes with chronic complications	Baseline characteristic - Clinical	Claims data	ICD-10 Diagnosis: E08.2x, E08.3x, E08.4x, E08.5x, E09.2x, E09.3x, E09.4x, E09.5x, E10.2x, E10.3x, E10.4x, E10.5x, E11.2x, E11.3x, E11.4x, E11.5x, E13.2x, E13.3x, E13.4x, E13.5x	Glasheen et al. (2019)

PFIZER CONFIDENTIAL

Redacted

Mild or moderate renal disease	Baseline characteristic - Clinical	Claims data	ICD-10 Diagnosis: I12.9, I13.0, I13.10, N03.x, N05.x, N18.1, N18.2, N18.3, N18.4, N18.9, Z94.0	Glasheen et al. (2019)
Severe renal disease	Baseline characteristic - Clinical	Claims data	ICD-10 Diagnosis: I12.0, I13.11, I13.2, N18.5, N18.6, N19.x, N25.0, Z49.x, Z99.2	Glasheen et al. (2019)
Hemiplegia or paraplegia	Baseline characteristic - Clinical	Claims data	ICD-10 Diagnosis: G04.1, G11.4, G80.0, G80.1, G80.2, G81.x, G82.x, G83.x	Glasheen et al. (2019)
Human immunodeficiency virus	Baseline characteristic - Clinical	Claims data	ICD-10 Diagnosis: B20.x	Glasheen et al. (2019)
Metastatic solid tumor	Baseline characteristic - Clinical	Claims data	ICD-10 Diagnosis: C77.x, C78.x, C79.x, C80.0, C80.2	Glasheen et al. (2019)
Any malignancy	Baseline characteristic - Clinical	Claims data	ICD-10 Diagnosis: C0x.x, C1x.x, C2x.x, C30.x, C31.x, C32.x, C33.x, C34.x, C37.x, C38.x, C39.x, C40.x, C41.x, C43.x, C45.x, C46.x, C47.x, C48.x, C47.x, C48.x, C49.x, C50.x, C51-C58.x, C60-C63.x, C76.x, C80.1, C81.x, C82.x, C83.x, C84.x, C85.x, C88.x, C9x.x	Glasheen et al. (2019)
Albumin serum	Baseline characteristic - Lab	Claims data	An event in the lab results table where the result_abbrev is albumin serum and result_units are g per dL	
ALT	Baseline characteristic - Lab	Claims data	An event in the lab results table where the result_abbrev is ALT and result_units are IU per L	
AST	Baseline characteristic - Lab	Claims data	An event in the lab results table where the result_abbrev is AST and result_units are IU per L	
Neutrophil count	Baseline characteristic - Lab	Claims data	An event in the lab results table where the result_abbrev is neutrophils count and result_units are thousand per μ L	

PFIZER CONFIDENTIAL

Redacted

Creatinine	Baseline characteristic - Lab	Claims data	An event in the lab results table where the result_abbrev is creatinine serum and result_units are mg per dL	
Hemoglobin	Baseline characteristic - Lab	Claims data	An event in the lab results table where the result_abbrev is hemoglobin and result_units are g per dL	

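### The code list for any non-hematological malignancy omits C64–C75, so this baseline row misses patients whose only solid-tumor codes fall in that range

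*Protocol*

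**What the plan says.** Section 9.3, Table 2 defines the row *Any non-hematological malignancy* as "Medical claim with an ICD-10 code in the IP or non-IP setting for non-hematological malignancies (dichotomous"), assessed from MM diagnosis to the day before index. The codes are left to Annex 2.

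The Annex 2 list for that row begins "C0x.x, C1x.x, C2x.x, C30.x, C31.x, C32.x, C33.x, C34.x, C37.x, C38.x, C39.x, C40.x, C41.x, C43.x, C45.x, C46.x, C47.x, C48.x, C49.x, C50" and finishes "C50, C51-C58.x, C60-63.x, C76.x, C80.1".

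Three other Annex 2 lists bear on the point:

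- *Other hematological malignancies*: "C81-C96, D46 (Excluding C90.0x").
- *Metastatic solid tumor*: "C77.x, C78.x, C79.x, C80.0, C80.2". Table 2 reports this as its own row, "Medical claim with an ICD-10 code in the IP or non-IP setting for metastatic solid tumor (dichotomous"), over the 180 days before index up to the index date.
- *Any malignancy*, a Charlson component, which ends "C51-C58.x, C60-C63.x, C76.x, C80.1, C81.x, C82.x, C83.x, C84.x, C85.x, C88.x, C9x.x".

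The non-hematological row and the Charlson rows cite the same comorbidity-index paper as their source.

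**The concern.** The row is labelled and defined as covering any non-hematological cancer, but the list behind it leaves out a continuous block of solid-tumor sites. An analyst who follows Annex 2 exactly will classify a patient with, say, only bladder cancer claims as negative. The protocol gives no reason for the gap.

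Describing clinical history is part of primary Objective 1. Section 9.9 warns that the light eligibility criteria may admit patients with other malignancies. For solid tumors, this row is the main place where a reader could judge how often that happened, in the elranatamab cohort and in the exploratory teclistamab cohort.

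A second, smaller issue is that the secondary-site codes sit only in the metastatic row. One patient can then be positive for metastatic solid tumor and negative for any non-hematological malignancy in the same table.

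**Working it through.** The protocol states no figure for this row, so there is none to reproduce. The check compares the code lists as sets of three-character ICD-10 categories.

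**Step 1. Expand the non-hematological list.** As printed it covers C00–C34, C37–C41, C43, C45–C58, C60–C63 and C76, plus the single code C80.1.

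**Step 2. Find what is absent between C00 and C80.** The absent categories are C35, C36, C42, C44, C59, C64–C75, C77–C79, and C80 apart from C80.1. The long block is C64–C75: 75 − 64 + 1 = 12 categories. The text runs without a break from C63 to C76, and the Charlson list shows the same jump, so this is not a redaction or a loss in text extraction.

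**Step 3. See whether another list picks up C64–C75.**

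| Annex 2 list | Codes relevant here | C64–C75 categories included |
|---|---|---|
| Any non-hematological malignancy | C60–C63, then C76, C80.1 | 0 of 12 |
| Any malignancy (Charlson) | C60–C63, then C76, C80.1, then hematological codes | 0 of 12 |
| Other hematological malignancies | C81–C96, D46, without C90.0x | 0 of 12 |
| Metastatic solid tumor | C77–C79, C80.0, C80.2 | 0 of 12 |

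**Step 4. Compare the metastatic list with the non-hematological list.** None of C77, C78, C79, C80.0 or C80.2 is in the non-hematological list, so the overlap is zero.

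**Step 5. Trace example patients through the two Table 2 rows.** All codes are dated after MM diagnosis and before index.

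| Solid-tumor codes on file | Non-hematological row | Metastatic row |
|---|---|---|
| C67.x only | no | no |
| C78.x only, within 180 days of index | no | yes |
| C78.x only, all more than 180 days before index | no | no |
| C78.x within 180 days, plus C34.x | yes | yes |

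The first line is the clear error. The second is the disagreement between rows. The third shows that, because of its shorter window, the metastatic row does not fully cover the gap. The fourth shows that a listed primary-site code is enough to count a metastatic patient.

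**Step 6. Size.** Let p be the share of patients with any non-hematological malignancy code, and f the fraction of those whose only such codes are C64–C75. From this gap alone the row reports p × (1 − f), so the relative undercount is f. The documents give neither p nor f. For scale only: section 9.5 reports 56 patients with an elranatamab claim, before eligibility and before later refreshes. If all 56 were in the cohort, each missed patient would lower the row by 1/56 = 1.8 percentage points.

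**The case against.** The strongest objections concern the metastatic codes. These patients are not hidden: metastatic solid tumor has its own Table 2 row. They are missed in the non-hematological row only if no listed primary-site code is on file, and nothing shows how often that occurs. The two rows use different windows and were not built to nest, so adding C77–C79 would not fully reconcile them. Adding them could also introduce error: in standard ICD-10, C79 includes secondary malignancy of bone, and in a myeloma cohort such a code may reflect myeloma bone disease rather than a second cancer. All of this stands. It makes keeping the secondary-site codes separate a defensible choice, provided the label says so.

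It can also be said that the row needs only one claim and that section 9.9 admits rule-out coding, which inflates prevalence. The net bias of the row is therefore unknown. That is fair, but miscoding in one direction does not justify a gap in the other, and the omission itself can only undercount.

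C44 is absent too, so restoring C64–C75 still does not make the row literally complete. That is also true; leaving out C44 may be deliberate, and the row should say whether it is.

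Finally, this is one descriptive row with no formal comparison behind it. That limits the weight of the point but not its correctness.

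**Conclusion.** The point holds for C64–C75. The list contradicts the row's own definition, no other malignancy list captures these 12 categories, and patients with only those codes are reported as free of non-hematological malignancy. That C64–C75 are solid-tumor sites is general ICD-10 structure; the protocol does not say so. The size of the undercount cannot be derived from the documents.

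For the secondary-site codes the conclusion is narrower: the two rows can disagree for the same patient, and the label does not warn the reader.

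Three stronger readings are not supported:

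- A reader might infer that patients with metastatic solid tumors are generally shown as having no solid tumor. The separate row and any listed primary-site code argue against that.
- A reader might infer a material distortion of the Charlson score, since its malignancy list has the same jump. That list also contains C9x.x, so the component will generally be met through the myeloma code itself, and the effect should be small.
- A reader might attach a percentage to the undercount. Any such figure would rest on invented inputs.

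This is a minor point. It touches a baseline description under a primary objective and leaves eligibility and outcomes untouched.

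**What to change.** 1. In the Annex 2 row for any non-hematological malignancy, replace the separate C60–C63 and C76 entries with C60–C76, and state whether leaving out C44 is intended.
2. Re-run that row for the elranatamab and teclistamab cohorts.
3. Check the Charlson *Any malignancy* list against its cited source. If the source includes C64–C75, correct the list; if it does not, leave it and note the difference from the baseline row.
4. Either add C77–C79, C80.0 and C80.2 to the baseline row or label the row as excluding secondary-site codes. If they are added, note that bone-metastasis codes may reflect myeloma bone disease. In either case, footnote that the metastatic row uses a different window.

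The cost is a code-list edit, one footnote or label, and a re-run of one baseline row per cohort, plus the Charlson score if step 3 changes it. At the date of version 2.0 (31 July 2025), refreshes 3 and 4 and the final report were still to come, so the change fits work already planned.
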